7.9.10. Index Hip Aspiration

Aspiration must be attempted prior to injection of study medication at Day 1 and prior to second injection of study medication. If effusion is detected by fluoroscopy guidance, withdraw to near dryness prior to injection.

7.9.11. Second Injection Criteria

Second Injection Inclusion and Exclusion Criteria must be assessed prior to administration of second injection of study medication. Please reference Section 7.4.4 and Section 7.4.5 for Second Injection Inclusion/Exclusion criteria listing. Please also reference Table 7-3.

7.9.12. Rescue Medication Dispensing and Accountability

Rescue medication (500 mg tablets of acetaminophen or paracetamol) will be dispensed to patients at the Screening visit. At each subsequent visit, at any time during the visit, rescue medication accountability will be performed. Additional rescue medication will be returned/dispensed as needed. Refer to Section 7.6.3 for further information regarding rescue medication.

7.9.13. Accurate Pain Reporting and Placebo Response Reduction Training

Placebo Response Reduction (PRR) Training

This training ("Participating in a Research Study, What you need to know," Analgesic Solutions, Wayland, MA) consists of a set of patient and staff educational materials for training on appropriate expectations of personal benefit while participating in a clinical trial. The purpose is to provide patients truthful information that will neutralize the potentially excessive expectations that drive high placebo responses in clinical trials. Patients will receive training at each study visit indicated in Table 7-2 and Table 7-3. The training video takes approximately 5 minutes to complete, and should be completed prior to any patient questionnaires.

All staff that have contact with patients must also complete the staff assigned PRR portion of the training prior to injection/dosing of patient.

Accurate Pain Reporting (APR) Training

The Accurate Pain Reporting Program ("Reporting Your Pain," Analgesic Solutions, Wayland, MA) consists of a set of patient and staff educational materials and instructions on how to accurately and reliably report pain scores, and on the proper use of pain intensity scales, with the aim of increasing patients' pain reporting accuracy. Staff training is conducted prior to the first subject visit. Patients will receive training at each study visit indicated in Table 7-2 and Table 7-3. The training video takes approximately 5 minutes to complete, and should be completed prior to any patient questionnaires.

All staff that have contact with patients must also complete the staff assigned APR portion of the training prior to injection/dosing of patient.

7.9.14. Patient Questionnaires

Questionnaires will be completed by the patient at each visit as scheduled (see Table 7-2 and Table 7-3). APR and PRR training will be completed first and then the patient will complete the

CONFIDENTIAL Page 53 of 72

questionnaires based on the sequence listed below in Table 7-6 and Table 7-7. All other assessments or procedures will occur after completion of the questionnaires.

Note: If Screening 1 and Screening 2 are combined into one visit (provided the patient does not have a washout from prohibited medications), please perform APR/PRR first, then the questionnaires in order they are shown below on Table 7-7, with the WOMAC being completed after APR/PRR, then all subsequent questionnaires completed as they are listed for Screening 1.

Table 7-6: Patient Questionnaires

Sequence at Visit	Screening 1	Screening 2	Day 1	Weeks 1, 4, 8	Week 12	Every 4 weeks during the OLE
1	PD-Q	WOMAC	WOMAC	WOMAC	WOMAC	WOMAC
2	PHQ-9			PGIC	PGIC	PGIC
3	GAD-7		SI	SI	SI	SI
4	PCS		HOOS-QOL	HOOS-QOL	HOOS-QOL	HOOS-QOL
5	ISI		EQ-5D-5L	EQ-5D-5L	EQ-5D-5L	EQ-5D-5L
6					TSQM-9	

Table 7-7: Patient Questionnaire Sequence if Screening 1 and Screening 2 Visits are Combined

Sequence at Visit	Screening 1 & Screening 2 (combined)		
1	APR/PRR Training		
2	WOMAC		
3	PD-Q		
4	PHQ-9		
5	GAD-7		
6	PCS		
7	ISI		

7.9.15. Review of Adverse Events and Concomitant Medications

After receiving assigned study medication and at all visits, the patient should be monitored for any AEs by the blinded assessor. Review of any Concomitant Medications should also be performed and documented in source documentation. Refer to Section 8.4.1 for further information in regard to reporting of AEs. Refer to Section 7.6 for further information in regard to allowed and restricted concomitant medication.

CONFIDENTIAL Page 54 of 72

8. ADVERSE EVENTS

Subjects will be monitored for adverse events from first dose of study medication through the end of their participation in the study.

Results of clinical safety assessments are to be recorded in the patient's medical records and transcribed to the appropriate eCRF, including the AE eCRF for clinically significant findings.

8.1. **Definitions**

Adverse Event (AE): An AE is any untoward medical occurrence in a patient or clinical investigation subject administered a pharmaceutical product and that does not necessarily have a causal relationship with this treatment.

An AE can therefore be:

- Any unfavorable and unintended sign (including an abnormal laboratory finding), symptom, or disease temporally associated with the use of a medicinal (investigational) product, whether or not related to the medicinal (investigational) product
- Any clinically significant abnormality found on an ECG, laboratory test, or physical examination
- Any worsening (i.e., any clinically significant adverse change in frequency and/or intensity) of a preexisting condition, which is temporally associated with the use of the medicinal (investigational) product

Pregnancy is not an AE; however, if a female patient or the female partner of a male patient who has received at least one dose of study medication becomes pregnant during the conduct of the study, the Investigator must notify the Sponsor according to the procedures in Section 8.4.1.

Serious Adverse Event (SAE): An SAE is any untoward medical occurrence that at any dose:

- Results in death
- Is life-threatening
 - o "Life-threatening" refers to an event in which the patient was at substantial risk of death at the time of the event; it does not refer to an event which hypothetically might have caused death if it were more severe
- Requires inpatient hospitalization or prolongation of existing hospitalization,
 - Note: Adverse events requiring hospitalizations that are less than 24 hours in duration do not meet this criterion. A planned hospitalization for an elective procedure or a preexisting condition that has not worsened during participation in the study does not meet this criterion
- Results in permanent or significant disability/incapacity; a substantial disruption of the patient's ability to carry out normal life functions
- Is a congenital anomaly/birth defect

CONFIDENTIAL Page 55 of 72

• Is an important medical event: event that may not be immediately life-threatening or result in death or hospitalization but may jeopardize the patient or may require intervention to prevent one of the outcomes listed in the definition above

Planned Hospitalization:

A hospitalization planned prior to first dose of study medication is considered a therapeutic intervention. If the planned hospitalization or procedure is executed as planned, it should be recorded in the patient's medical history. However, if complications arise during the planned hospitalization or procedure or the patient experiences an AE during the planned hospitalization or procedure, it must be reported as an AE.

8.2. Monitoring of Adverse Events

Each patient will be monitored for the occurrence of AEs, including SAEs, beginning with administration of the first dose of study medication. Each patient will be followed for safety monitoring until the last follow up visit in the trial as described in the Schedule of Assessments.

Patients will be questioned and/or examined by the Investigator or a qualified designee for evidence of AEs. The questioning of patients with regard to the possible occurrence of adverse events should be generalized such as, "How have you been feeling since your last visit?" The presence or absence of specific AEs should not be elicited from patients.

Results of study efficacy assessments and patient reported outcome surveys should not be reported as adverse events unless they indicate a significant worsening from baseline.

The Investigator is required to follow SAEs until resolution or withdrawal of consent. Resolution is defined as:

- A return to baseline for a pre-existing condition
- Resolved with or without residual effects
- The Investigator does not expect any further improvement or worsening of the event
- Fatal outcome: If an autopsy is performed on a deceased patient, the autopsy report should be provided to the Sponsor as soon as it is available

8.2.1. Monitoring of Laboratory Assessments and Other Diagnostic Tests

The Investigator will review results of laboratory and other diagnostic tests for clinical significance and consideration as an AE.

8.2.2. Adverse Events That Occur During the Injection Procedure

If an adverse event occurs during the injection procedure, the Unblinded Injector will record the details of the AE in the patient's chart and provide a full report of the event to the Blinded Assessor in a blinded manner. Any difficulties with the study drug administration should not be reported to the Blinded Assessor unless it is a direct cause of an AE. For any difficulties with the study drug, the Unblinded Injector should refer to the Pharmacy Binder.

CONFIDENTIAL Page 56 of 72

8.2.3. Reporting Arthralgia in the Index Hip

Since all enrolled patients are required to have a certain level of arthralgia in the index hip before they receive study drug, the Investigator must take care to fully assess any patient reports of index hip arthralgia that occurs during the study. Incremental return of preexisting index hip arthralgia following post-injection pain relief does not meet the criteria for an adverse event, unless the arthralgia is clinically significantly worse from baseline (before study drug administration).

8.3. Assessment of Adverse Events

8.3.1. Assessment of Seriousness

Each adverse event should be assessed for seriousness against the definition of Serious Adverse event in Section 8.1 above.

8.3.2. Assessment of Severity

Each adverse event should be evaluated for severity or intensity. This is not the same as "serious," which is based on patient/event outcome or action criteria usually associated with events that pose a threat to a patient's life or functioning. The severity of AEs will be assessed according to the following definitions:

- Mild: the AE is noticeable to the patient and/or the Investigator, but does not interfere with routine activity
- Moderate: the AE interferes with routine activity, but responds to symptomatic therapy or rest
- Severe: the AE significantly limits the patient's ability to perform routine activities despite symptomatic therapy

8.3.3. Assessment of Relationship to Study Medication

A medically qualified Investigator must assess the relationship of any AE (including SAEs) to the use of the investigational product, as **related** or **not related**, based on clinical judgment and using all available information, and may include consideration of the following factors:

- Possible alternative causes of the AE, including the disease under treatment, pre-existing conditions, concomitant use of other drugs, and presence of environmental or genetic factors
- The temporal association between drug exposure and onset of the AE
- Whether the manifestations of the AE are consistent with known actions or toxicity of the investigational product

The causal relationship between the study medication and the AE will be assessed using one of the following categories:

CONFIDENTIAL Page 57 of 72

Not Related: An AE is not associated with study medication if:

- Temporal relationship is lacking (e.g., the event did not occur within a reasonable time frame following administration of the study medication); *or*
- Other causative factors more likely explain the event (e.g., a pre-existing condition, other concomitant treatments)

Related: An AE is attributed to the study medication if:

- There is a positive temporal relationship (e.g., the event occurred within a reasonable time frame following administration of study medication); *and*
- The AE is more likely explained by the investigational product than by another cause (e.g., the AE shows a pattern consistent with previous knowledge of the investigational product or the class of the investigational product)

8.4. Recording of Adverse Events

All AEs, regardless of seriousness, severity, or causal relationship to study medication, will be recorded on the AE page of the eCRF.

When possible, adverse events should be reported as a specific disease or syndrome rather than individual signs and symptoms. Additionally, procedures and diagnostic tests results should not be reported as AEs unless their underlying diagnosis is unknown. For example, the diagnosis of 'influenza' should be reported as an AE instead of the symptoms of fever, fatigue, malaise, and positive flu test when the Investigator believes that those are all associated with influenza.

However, if an observed or reported sign, symptom, or clinically significant laboratory anomaly is not considered by the Investigator to be a component of a specific disease or syndrome, then it should be recorded as a separate AE on the appropriate AE eCRF.

8.4.1. Reporting of Serious Adverse Events

When an SAE occurs, the Investigator or designee, must log into the electronic data capture (EDC) system and complete the SAE report form within 24 hours of becoming aware of the SAE. The EDC system will notify the Medical Monitor and other appropriate study personnel of the SAE.

If the EDC SAE form is not available, the Investigator should complete and sign the paper SAE form and email it to the Sponsor. When the EDC system is available again, the SAE should be input into the EDC SAE form.

Follow up information relating to an SAE must be reported to the Sponsor within 24 hours of receipt by the Investigator by entering new or updated information into the EDC SAE form.

All SAEs that occur at your site should, in addition, be reported by the Investigators to the responsible IRB/EC without undue delay, if applicable according to IRB/EC requirements.

During the conduct of the study, the Sponsor will provide expedited safety reports (AEs classified as serious, unexpected and related to study medication) to the investigative sites. If this occurs, the investigative site must report the information to their IRB per local guidelines (may be submitted by the Sponsor or designee for sites that use a central IRB).

CONFIDENTIAL Page 58 of 72

8.4.2. Unblinding Treatment for a Patient during the Trial

Requirements for emergency unblinding by the Investigator are detailed in Section 7.5.9. To assess an occurrence of a serious adverse event for regulatory reporting purposes, Flexion Pharmacovigilance or Regulatory Operations may unblind the treatment of any subject.

8.5. Safety Monitoring Roles

The site personnel will carefully monitor each patient throughout the study for possible AEs. All AEs will be reviewed and assessed by the Blinded Assessor. All AEs will be documented on the eCRF and will be followed until either completely resolved or until a stable chronic outcome is determined by the Principal Investigator. SAEs will be reported in accordance with Section 8.4.1. The Medical Monitor must promptly review all information relevant to the safety of an investigational new product received from any source. The Medical Monitor will also review alert laboratory results in real time and will contact Investigators as needed to ensure that issues are managed in an appropriate manner.

The Medical Monitor and the Sponsor will review blinded AE data approximately on a quarterly basis, accessed through the EDC system and associated reporting tools, in order to identify potential safety issues/trends that may not be apparent through individual AE reporting. If systematic review identifies a pattern of concern, Sponsor will take steps to address the issues including but not limited to modifying the protocol and/or notifying investigator, authorities and IRB/ECs. Each review will be documented and filed in the Trial Master File.

Investigators will receive prompt notification of any adverse experience associated with the use of the study medication that is both serious and unexpected, or any finding that suggests a significant risk for patients. The Investigator will promptly inform the IRB/EC of the notification and insert the notification in the Investigator's Regulatory Binder in accordance with local regulations.

8.6. Clinical Management of Index Hip-Related Events

In the event that the patient has an immediate reaction following administration of study medication or returns to the clinic with an acute exacerbation (e.g., tenderness, increased pain, swelling, effusion, decreased mobility of the index hip), the patient should be treated according to local clinical guidelines and physician experience.

If the index hip is aspirated at any time other than administration of study medication for any reason, the volume of synovial fluid aspirated must be documented, synovial fluid should be (1) cultured, (2) evaluated for presence of crystals and (3) assessed for white cell count at a local laboratory, and the results should be documented.

Any event that is a change from the patient's baseline status (new or worsening case) should be reported as an AE and those meeting the definition of serious must be reported in accordance with Section 8.4.

CONFIDENTIAL Page 59 of 72

8.7. Pregnancy

All pregnancies, female patients or female partners of male patients during the study, must be reported within 24 hours on the Pregnancy Report Form. The Investigator must continue to follow the pregnancy until the completion of the pregnancy, including the outcome and the condition of the newborn (if applicable). If not all information on the Pregnancy Report Form is available at the time of the initial report, follow-up reports should be provided to the Sponsor in a timely manner. Additional subsequent follow-up is not needed when a newborn baby is healthy.

CONFIDENTIAL Page 60 of 72

9. STATISTICAL CONSIDERATIONS

9.1. Statistical and Analytical Plans

A comprehensive statistical analysis plan (SAP) will be written and approved for Part I and Part II prior to database lock for each part of the study. If, after the study has been completed, changes are made to the SAP referenced below, these deviations to the plan will be listed, along with an explanation as to why they occurred, in the Clinical Study Report (CSR). The key aspects of the proposed analyses are summarized below. Parts I and II of the study will enroll separate patients, and as such all analyses will be performed independently of one another. Analyses for Parts I and II of the study will be performed in the same manner, as detailed below. The analyses of the Part I data will be performed in an unblinded manner and results may be used to inform the conduct of Part II; as the analyses of Part I will be completed prior to the enrollment of any patients in Part II, this will have no impact on maintaining the blind for Part II.

9.1.1. Planned Analyses

Part I Analysis

An unblinded analysis will be conducted when all Part I patients have completed the study. All data collected on Part I patients will be analyzed. All analyses of the Part I data are exploratory in nature.

Part II Interim Analysis

An unblinded interim analysis will be conducted when all Part II patients have completed the double-blind phase of the study.

Final Analysis

A final analysis will be conducted when all Part II patients have completed the OLE phase of the study. Final analyses specified in the protocol and SAP will be completed and reported in the CSR. Post-hoc, exploratory analyses, may be completed to further understand and elucidate study results. Any post-hoc, exploratory, analyses completed will be clearly identified as such in the final CSR.

9.2. General Considerations and Methods

Data collected in this study will be presented using summary tables, figures, and subject data listings. Summary tables will present data by treatment group and, if applicable, by time of collection. Continuous variables will be summarized using descriptive statistics, specifically the mean, median, standard deviation, minimum and maximum. Categorical variables will be summarized by frequencies and percentages. Confidence intervals may also be provided. Figures will be used to support the presentation of certain data. Sensitivity analyses may be performed to examine the effect of missing data, as well as the effect of Baseline imbalance, should one occur.

All confidence intervals (CIs), statistical tests, and resulting p-values will be reported as 2-sided. Significance will be assessed at $\alpha = 0.05$ level.

CONFIDENTIAL Page 61 of 72

9.2.1. Analysis Populations

The following analysis populations are planned for each part of this study as follows:

- Full Analysis Set (FAS) Population: All patients who received study drug. The FAS population will be used to examine efficacy endpoints for the double-blind phase of the study
- Safety Population: All subjects who received at least one dose of study drug. The Safety Population will be used to assess safety and tolerability
- Second Injection Population (Part II only): All patients who received a second injection. The Second Injection Population will be used to examine efficacy endpoints in the openlabel extension phase of the study
- Per Protocol Population (Part II Only): All patients in the FAS population who completed the Week 12 visit with no major protocol deviations that may impact the evaluation of the primary efficacy endpoint based on blinded data prior to unblinding of the double-blind phase data.

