7. INVESTIGATIONAL PLAN

7.1. Overall Study Design and Plan

This is a two-part, multi-center, randomized, double-blind, placebo-controlled, parallel-group study in patients with hip OA. Approximately 70 patients will be enrolled in Part I and approximately 440 patients will be enrolled in Part II of the study. In each part, patients will be randomized to one of two treatment groups (1:1) and treated with a single IA injection of either 32 mg FX006 or normal saline.

Eligible patients will be randomized within strata defined by Baseline Western Ontario and McMaster Universities Osteoarthritis Index (WOMAC) A (pain) (0-10 numeric ratings scale (NRS) average of Screening 2 and Day 1 with the following classifications: 5.0 to < 6.0, 6.0 to < 7.0, and $\geq 7.0 \text{ to} 9.0$ (see Section 9 for details).

FX006 or saline placebo will be administered as a single IA injection with a 12-week follow-up period in the double-blind phase.

Patients participating in Part I of the study will be treated with a single IA injection of either 32 mg FX006 or normal saline and will return for follow up visits at Weeks 12, 16, 20, and 24 or up until the time of this amendment. The patients will be discontinued at the time of notification by the Investigator.

Patients participating in Part II of the study will be treated with a single IA injection of either 32 mg FX006 or normal saline and will return for follow up visits at Weeks 12, 16, 20, and 24. Patients who are eligible for the second injection in the open-label phase at Week 12 will receive an open-label injection of FX006 at Week 12 and return for follow-up visits at Weeks 16, 20, and 24. These patients will complete the study at Week 24.

Patients participating in Part II of the study that are not clinically indicated for a second injection at Week 12 will return to the clinic at Weeks 16, 20, and 24 and will receive an open-label injection of FX006 at the first evaluation where the patient has been determined to meet all criteria. Patients will then return for follow-up visits every 4 weeks for 12 weeks post second injection and will complete the study 12 weeks post second injection (e.g., Week 24, 28, 32, or 36 depending on when the patient receives the open-label injection).

Patients participating in Part II of the study who are not eligible for a second injection after evaluation at Weeks 12, 16, 20, and 24 will complete the study at the Week 24 visit and complete the End of Study (EOS) assessments.

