9.2.3.2. Key Secondary Efficacy Endpoints

- Change from Baseline on the WOMAC C (function) score at Week 12
- PGIC score at Week 12

9.2.3.3. Additional Secondary Efficacy Endpoints:

- Area Under the Effect curve (AUE) of change from Baseline on the WOMAC A (pain) subscale over the time intervals (e.g., Weeks 1 to 4, Weeks 1 to 8, and Weeks 1 to 12)
- AUE of change from Baseline on the WOMAC C (function) score over the time intervals (e.g., Weeks 1 to 4, Weeks 1 to 8, and Weeks 1 to 12)
- PGIC at Weeks 1, 4, and 8
- Change from Baseline on the WOMAC A (pain) score at Weeks 1, 4, and 8
- Change from Baseline on the WOMAC C (function) score at Weeks 1, 4, and 8
- Change from Baseline on the WOMAC B (stiffness) score at Weeks 1, 4, 8, and 12
- Change from Baseline on the WOMAC total score at Weeks 1, 4, 8, and 12
- Percent of responders (defined as patients with high improvement in pain or function) according to OMERACT-OARSI criteria at Weeks 1, 4, 8, and 12
- Proportion of patients experiencing a ≥20%, ≥30%, or ≥50% decrease in WOMAC A
 (pain) at Weeks 1, 4, 8, and 12
- Rescue medication use at Weeks 1, 4, 8, 12 and total consumption
- Change from Baseline on the SI at Weeks 1, 4, 8, and 12
- Change from Baseline on the EQ-5D-5L at Weeks 1, 4, 8, and 12
- Change from Baseline on the HOOS-QOL at Weeks 1, 4, 8, and 12
- TSOM-9 at Week 12
- Change from Baseline on WOMAC A (pain), B (stiffness), C (function) and PGIC at Weeks 1, 4, 8, and 12 in patients with unilateral hip OA

The same endpoints as above will be examined post Week 12 during the OLE phase of Part II with the addition of the following:

• Time to second injection for patients who receive a second injection of FX006

CONFIDENTIAL Page 63 of 72

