9.3. Determination of Sample Size

9.3.1. Sample Size Considerations

Approximately 70 patients will be randomized in Part I and approximately 440 patients will be randomized in Part II in this study (an estimated 35 and 220 per treatment group respectively.)

For Part I, a sample size of approximately 35 per arm will provide information regarding the treatment effect. For Part II of the study, the expected sample size was determined based on the primary endpoint as follows. A minimum sample size of N=212 per arm for the placebo and the FX006 group has 90% power to yield a statistically significant difference (alpha=0.05, 2-sided) if the true underlying difference at Week 12 is 0.65 and with an assumption of 2.0 for the SD. For the first key secondary endpoint, the sample size of N=220 per treatment group has 90% power to yield a statistically significant difference between FX006 and placebo if the true underlying difference is 0.68 at Week 12, assuming a SD of 2.125. An early discontinuation rate of 6% was assumed. The data from Part I may be used to inform if the above assumptions were appropriate and the planned sample size for Part II should remain at 440, or whether a smaller sample size would be feasible.

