9.4.3. Efficacy Analyses

Primary Efficacy Analysis

The primary endpoint will be analyzed with a longitudinal mixed model for repeated measures (MMRM) with fixed effects for treatment group, study week, treatment-by-week interaction and Baseline score. Subject will be the random effect. Treatment differences from control will be estimated via least square means from the analysis model along with 95% confidence intervals, and associated 2-sided p-values. This model assumes missing at random and includes only observed data.

Secondary Efficacy Analyses

Key secondary endpoints will be assessed similarly to the primary endpoint. Multiplicity will be addressed by analyzing the key secondary endpoints sequentially in the order presented in the protocol, testing each endpoint at the nominal alpha=0.05, 2-sided level to ensure overall type I error control at the 2-sided 0.05 level.

Additional continuous secondary efficacy endpoints will also be assessed similarly to the primary endpoint, but are not part of the sequential testing approach. Categorical end points will be compared via chi-square or exact tests depending on incidence rates.

AUE will be calculated and comparisons of the AUE endpoints will be estimated from an Analysis of Covariance (ANCOVA) with model parameters for treatment and covariates of Baseline WOMAC A score and study site. Full details of the AUE analyses will be detailed in the SAP.

Efficacy Analyses For The Open-Label Extension Phase (Part II)

Exploratory efficacy endpoints for the open-label extension phase will be analyzed similarly to the primary and secondary endpoints, but separately for the time period prior to the second injection and the time period post the second injection. Time-to-event endpoints will be assessed via log-rank tests and results will be presented in Kaplan-Meier plots.

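### In Part II, the comparison of arms after Week 12 and before the second injection falls to patients selected by that later injection, and never re-injected patients' Weeks 16–24 scores belong to no efficacy population.

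*Protocol*

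**What the plan says.** Protocol 9.2.1 defines the FAS as everyone who received study drug and ties its efficacy use to the double-blind phase. Table 7-2, footnote a, ends that phase at Week 12. For the next phase of Part II, 9.2.1 says: "The Second Injection Population will be used to examine efficacy endpoints in the openlabel extension phase of the study". That population is the patients who received a second injection. The Per Protocol Population is tied to the Week 12 primary endpoint.

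The end of 9.2.3.3 states: "The same endpoints as above will be examined post Week 12 during the OLE phase of Part II". Section 9.4.3 calls these endpoints exploratory and says they will be analysed "separately for the time period prior to the second injection and the time period post the second injection". It names no population.

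Patients who are never re-injected are still followed. Under 7.1, those "not eligible for a second injection after evaluation at Weeks 12, 16, 20, and 24 will complete the study at the Week 24 visit". Table 7-3 schedules WOMAC, PGIC, sleep interference, HOOS-QOL and EQ-5D-5L at the post-Week 12 visits. A second injection requires, among other criteria in 7.4.4, a WOMAC A score of at least 3 and a clinical indication in the opinion of investigator and patient.

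The supplied SAP covers Part I only. Its section 4.10.1.1 puts all study weeks into the FAS model, and its section 3.1 keeps only pre-second-dose FAS data for the one Part I patient who had a second dose.

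**The concern.** Membership of the Second Injection Population is decided after randomisation, partly by the outcome under analysis. If FX006 changes pain after Week 12, it also changes who enters that population and when. The two arms inside it are then no longer comparable groups, even at visits before the injection.

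The patients left out include those whose pain stayed below 3 through Week 24. Longer duration of effect is the reason given for studying the product in the hip (5.2.2), and these are the visits that bear on it. The plan collects the scores and then assigns them to no efficacy analysis.

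The protocol also says that Parts I and II will be analysed in the same manner (9.1, 9.4). Part I keeps its later visits in the FAS; Part II, as written, does not.

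**Working it through.** **The plan's own figures.** Section 9.3.1 states, at "alpha=0.05, 2-sided": "A minimum sample size of N=212 per arm for the placebo and the FX006 group has 90% power" "if the true underlying difference at Week 12 is 0.65 and with an assumption of 2.0 for the SD". With n = 2(z₀.₉₇₅ + z₀.₉₀)²SD²/d² and z values 1.960 and 1.282:
- Primary: 2 × 3.242² × 2.0² / 0.65² = 199 evaluable per arm; 199/0.94 = 211.7, so 212.
- First key secondary ("if the true underlying difference is 0.68 at Week 12, assuming a SD of 2.125"): 206 evaluable; 206/0.94 = 219.1, so 220.

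Both reproduce. They concern Week 12 and do not depend on the present point. They supply the 0.65, the SD of 2.0 and the 6% loss used below.

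**What follows from the text alone.** WOMAC is completed before any other assessment at a visit (Table 7-3, footnote m), so the injection-visit score is a pre-injection score. Within the Second Injection Population:
- Week 16 pre-injection data come only from patients injected at Week 16, 20 or 24.
- Week 20 data come only from those injected at Week 20 or 24.
- Week 24 data come only from those injected at Week 24, so every WOMAC A score there is at least 3 by rule, in both arms.

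The selection needs no assumption. Its numerical effect does.

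**Assumed scenario.** Placebo mean WOMAC A 4.0, FX006 3.35, SD 2.0, within-patient correlation 0.75, scores kept within 0–10. A patient is re-injected at the first of Weeks 12, 16, 20 and 24 where the score is at least 3 and a chance draw with the stated uptake succeeds. The waning case has effects of 0.40, 0.20 and 0 at Weeks 16, 20 and 24.

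| Difference, placebo minus FX006 | Week 16 | Week 20 | Week 24 |
|---|---|---|---|
| Sustained effect: true | 0.62–0.63 | 0.62–0.63 | 0.62–0.63 |
| Second Injection Population, uptake 60–80% | 0.36–0.37 | 0.26–0.33 | 0.12–0.23 |
| Waning effect: true | 0.38–0.39 | 0.19–0.20 | 0.00 |
| Second Injection Population, uptake 60% | 0.38 | 0.25 | 0.08 |
| Second Injection Population, uptake 80% | 0.38 | 0.18 | −0.02 |
| Second Injection Population, uptake 100% | 0.14 | 0.01 | −0.07 |

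Repeat simulations of the sustained case agree to within about 0.03.

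**Patients left out.** In the sustained case 17–22% of placebo and 26–32% of FX006 patients are never re-injected. With 220 × 0.94 ≈ 207 per arm reaching Week 12, that is 207 × (0.17 + 0.26) ≈ 89 to 207 × (0.22 + 0.32) ≈ 112 of 414.

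**Wider assumptions.** Placebo mean was 3.5, 4.5 or 5.0, correlation 0.7 and uptake 50–100%; the effect was either uniform or confined to 25% of patients.
- Sustained effect: the Second Injection Population reads 0.02–0.52 against a true 0.55–0.65, low in every scenario.
- Waning effect: 0.13–0.58 at Week 16 (true 0.36–0.40), −0.02 to 0.33 at Week 20 (true 0.18–0.21) and −0.29 to 0.11 at Week 24 (true about 0).

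**Candidate remedies.**
- A raw comparison of all patients not yet injected reads 0.17–1.04 against 0.55–0.65 under a sustained effect, so it is not adequate.
- A sequential-regression estimate on all patients, using earlier scores and stopping at injection, gives 0.62–0.63 in the sustained 60–80% scenario. With a waning effect it missed by up to about 0.10 (−0.10 against 0 at Week 24, uptake 80%).
- When uptake was also made to depend on the patient's unrecorded coming course, the same estimator gave 0.30–0.50 against a true 0.62–0.64.

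**The case against.** The best defence is that this is unfinished detail. Section 9.4.3 names no population for the pre-injection period, and full details are deferred to a Part II SAP that is not among the documents. The endpoints are exploratory. The open-label efficacy objective (6.3) concerns response after a second injection, which the Second Injection Population fits.

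The limits on importance stand. The deferral does not remove the point: 9.2.1 states a rule for open-label efficacy, 9.2.3.3 places post-Week 12 endpoints in that phase, and a SAP that follows both would carry out the selected comparison.

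A reader might go further in four ways that the documents do not support:
- **The bias runs toward no effect.** That holds in the simulations with a sustained benefit. Section 5.2.1 describes delivery over approximately 3 months, so waning after Week 12 is plausible, and the bias can then be near zero or of either sign.
- **The data are analysed nowhere.** Section 9.2 promises summaries and listings of collected data, and the Safety Population includes these patients.
- **All post-Week 12 efficacy in the trial is affected.** Part I is not; its FAS model takes every study week.
- **Those left out are all durable responders.** Some will have failed another second-injection criterion.

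**Conclusion.** The point holds for Part II. Followed as written, the protocol compares randomised arms within a group defined by a later, partly pain-driven event, and gives never re-injected patients' Weeks 16–24 scores no efficacy population. This rests on the text.

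The size rests on assumptions. If the effect is sustained, about two fifths of a 0.63 difference is lost at Week 16 (0.36/0.63 = 57% and 0.37/0.63 = 59% remain). Between about two thirds and four fifths is lost at Week 24 (0.23/0.63 = 37% and 0.12/0.63 = 19% remain). If the effect wanes, neither size nor direction can be stated in advance.

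This should be corrected, but it does not threaten the trial's main conclusions. The Week 12 primary and key secondary analyses, their type I error control and the sample size are untouched.

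**What to change.** In 9.2.1 and the Part II SAP, limit the Second Injection Population to efficacy after the second injection.

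For post-Week 12 visits up to and including the pre-injection assessment, use the Part II FAS. Fit one MMRM with the double-blind visits through Week 24, excluding data after the second injection. SAP 3.1 already applies that cut to the Part I patient who had a second dose. Name this population in 9.4.3.

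State that the model estimates the arm difference had no second injection been given, and that it assumes missing at random: re-injection depends on recorded scores. Because the decision also rests on judgment, add a sensitivity analysis, for example imputing excluded values with a range of shifts by arm. Do not substitute a raw comparison of patients not yet injected.

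The cost is a wording change, one more model with its sensitivity analysis, and reliance on an assumption that the data cannot verify. No new data are needed, and the Part II SAP is due only before database lock.
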